### 11.2.4 Determination of Sample Size

Three hundred (300) male and female patients will be enrolled into the study. In a randomized study of two iron chelators for the treatment of iron overload in patients with sickle cell disease (Vichinsky et al., 2006), mean  $\pm$ SD reductions of  $4.0 \pm 1.5$  mg/g dw and  $4.5 \pm 2.0$  mg/g dw were observed (Figure 1 of the article, numerical values obtained from the authors) in patients from the baseline LIC categories of  $>7$ - $14$  mg/g dw or  $>14$  mg/g dw after they were treated with 35-50 mg/kg or  $\geq 50$  mg/kg of deferoxamine respectively, for 52 weeks. Assuming the same mean reduction in LIC for deferiprone but a higher SD of  $\pm 4.0$  mg/g dw for both treatments due to possibly higher variability associated with MRI measurement, the sample size of 300, with  $>80\%$  being patients with sickle cell disease, will provide over 95% power for demonstrating non-inferiority of deferiprone to deferoxamine in patients with sickle cell disease.

The sample size estimate is based on a non-inferiority margin of 2 mg/g dw for the reduction of LIC and an alpha of 0.05, two-sided (or an alpha of 0.025, one-sided, Appendix 18.5). It has been reported that in a typical patient with thalassemia major, the LIC could increase by 5 mg/g dw after 1 year without chelation therapy. As the cause of iron overload is the same in thalassemia and sickle cell disease, the same increase in LIC may be expected in patients with sickle cell disease who are transfused at the same rate and not treated with a chelator. Hence, the difference in reduction of LIC between deferoxamine therapy and a placebo (effect size) can be estimated to be 9 (i.e., 4 – (-5)) mg/g dw. This means that the non-inferiority margin of 2 mg/g dw would be about 20% of the effect size.

With the enrolment of 300 patients, there is also greater than 99% chance (power) of occurrence of at least 1 adverse event with an anticipated incidence rate of 2%, or greater than 95% chance for an anticipated incidence rate as low as 1%.

### 11.2.5 Study Populations

Study populations intended for analysis will be defined as follows: Intent-to-Treat (ITT), Per-Protocol (PP), and Safety. The ITT population will represent the primary analysis population to evaluate the treatment groups on all efficacy endpoints. The primary efficacy endpoint will also be analyzed for the PP population, which is the secondary analysis population.

#### 11.2.5.1 Intent-to-Treat

The ITT population will include all randomized patients who received at least one dose of study drug and have a baseline and at least one post-baseline efficacy assessment. All efficacy analyses will be based on the ITT population.

#### 11.2.5.2 Per-Protocol

The Per-Protocol (PP) population will include all enrolled patients who complete the study, have no major protocol violations, and have an efficacy rating at the end of the study. Prior to database lock, major protocol violations will be reviewed and excluded from the PP population. Major protocol violations will include (but not be limited to) the following:

- Patients who did not fulfill the LIC  $> 7$  mg/g inclusion criterion.
- Patients who were not compliant with the treatment (<80% compliance).
- Patients who took iron chelator medications other than the assigned study medication during the course of the study.

Only the primary efficacy analysis will be performed with the PP population.

#### 11.2.5.3 Safety

The Safety population will include all enrolled patients who took at least one dose of study drug.

### 11.3 Statistical Plan

A separate detailed statistical analysis plan (SAP) will be prepared and approved before database lock. Any changes in the planned statistical methods after database lock will be documented in the final clinical study report.

### 11.4 Definition of Analysis

For patients who were terminated from the study prior to Month 12, if their last efficacy measures were obtained within 30 days of Month 12, the data obtained will be treated as the Month 12 data. For early termination that occurred outside this window, the last observation carried forward (LOCF) method will be used to fill the missing data when the early termination was not caused by worsening of disease conditions or inadequate efficacy of the drug. For early termination due to worsening of disease conditions or inadequate efficacy of the drug, as indicated in the eCRF, the “worst value” method will be used. That is, the worst value of all patients for the corresponding treatment group will be used to impute the missing data at that time point. For missing data due to missed visit, the LOCF method will be used to fill the void.

As a sensitivity analysis, the analysis will be repeated with the LOCF method being used for all drop-out patients in the deferoxamine group. Other sensitivity analyses, where appropriate, will be detailed in the SAP.

For safety data analysis, no imputation will be performed on the missing data, and analysis will be based on observed cases (OC).

### **11.4.1 Planned Analyses**

#### **11.4.1.1 Patient Disposition and Drug Exposure**

Patient disposition will be summarized and presented, including the number and percentages of patients who were screened, enrolled, received at least one dose of study medication, completed the study, and withdrew (including reasons for withdrawals). The proportions of drop-outs will be compared between the deferiprone group and the deferoxamine group using Fisher's exact test.

For each patient, the number of doses taken will be computed from the study drug dispensing and accountability eCRFs obtained at each visit. The extent of exposure to the study medication, the number of doses, and the total dose taken during the study will be summarized with descriptive statistics.

#### **11.4.1.2 Patient Characteristics**

Baseline characteristics will be summarized by: mean, standard deviation, minimum, median and maximum values (by ITT and PP populations). Medical history, prior and concomitant medications will be summarized descriptively (number of patients and percentage).

#### **11.4.1.3 Efficacy Analyses**

##### **Primary Efficacy Endpoint**

The change from baseline to Week 52 in LIC will be compared between the two treatment groups using an analysis of covariance (ANCOVA) model, including treatment variable as the main factor and total transfusional iron input during the study and baseline LIC as covariates. The 95% confidence interval (CI) of the difference (deferiprone minus deferoxamine) in change of LIC from baseline to Week 52 between the two treatment groups will be computed. For the demonstration of non-inferiority, the upper limit of the 95% CI should be no more than 2 mg/g dw.

##### **Secondary Efficacy Endpoints**

The change from baseline to Week 52 in patient-reported quality of life (SF-36 or Child Health Questionnaire) will be compared between the two treatment groups. Detailed information on the statistical method to be used will be provided in the statistical analysis plan. The change from baseline to Week 52 in cardiac MRI T2\* and serum ferritin will be compared between the two treatment groups using an ANCOVA model, with treatment variable as the main factor and total transfusional iron input during the study and baseline cardiac MRI T2\* or serum ferritin as covariates. As with LIC, the 95% CI of the difference between the two treatment groups will be computed for both MRI T2\* and serum ferritin. The MRI T2\* data will be log-transformed before any statistical testing.

The longitudinal data of patient-reported quality of life, LIC, cardiac MRI T2\*, and serum ferritin will also be analyzed for time trend by using the appropriate mixed model,

or its equivalent for the quality of life data. Transfusional iron input will be assessed and compared among treatment groups and hematologic diagnoses. .

#### Subgroup analysis:

The comparison of the two treatment groups for the primary and secondary efficacy endpoints will be performed in:

- SCD patients only;
- non-SCD patients.

More subgroup analysis, where appropriate, may be defined in the SAP.

#### 11.4.1.4 Safety Analyses

All safety data collected will be presented in listings and summary tables to give an overview of the safety findings.

#### Adverse Events

A summary table of adverse events will include the following information:

- number of patients exposed to study treatment,
- number of patients experiencing at least one AE,
- number of patients experiencing at least one severe AE,
- number of patients experiencing at least one serious AE,
- number of patients experiencing at least one drug-related AE,
- number of deaths,
- total number of patients withdrawn (and reason for withdrawal) and
- number of withdrawals due to an AE.

All adverse experiences will be coded using MedDRA. Adverse events will be defined as: 1) AEs that occurred or worsened (increased in severity and/or frequency) on or after the first dose of study medication. 2) AEs with a missing start date and a stop date on or after the first dose of study medication. 3) AEs with both a missing start and stop date. AEs will be summarized by treatment and by MedDRA system organ class (SOC) and Preferred Term. SAEs that occurred within 14 days after treatment discontinuation will be considered treatment-emergent AEs. Serious adverse events that occurred within 30 days after treatment discontinuation will be included in the database.

Adverse events will be summarized by treatment group using the total number of AEs, the total number and percent of patients who experience an AE, and the number and percent of patients who experienced an AE within each SOC (and preferred term within an SOC). AEs will also be presented by severity (mild, moderate, severe), by seriousness (serious, non-serious) and by relationship to study medication (at least possibly related, not related). The number of patients withdrawn will also be presented.

To count the number of patients who experienced each AE, patients who experienced the same AE multiple times will only be counted once for the corresponding preferred term. Similarly, if a patient experiences multiple AEs within the same SOC, that patient will be counted only once for that SOC. AEs will be tabulated presenting the SOC alphabetically, and within each SOC, preferred terms will be presented in decreasing order of the total number of patients who experienced each AE. In summaries presenting the incidence of AEs by severity, seriousness, and relation to study medication, a patient with multiple events coded to a given preferred term or SOC will be counted once for that preferred term or SOC according to the most severe event, the most serious event, or the event with the closest relationship to study medication.

A listing of serious adverse events and a listing of withdrawals due to AEs will be presented. Patient deaths will be listed separately and discussed with patient narratives.

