In the sickle cell centres of the Cardeza Foundation and Thomas Jefferson University Hospital, approximately 50% of the patients with SCD admitted to the hospital received an average of 10 units of RBCs per year; 17% to 37% of these patients developed iron overload. Compared to the non-iron-overloaded group, the iron-overloaded patients with serum ferritin level  $> 1,500 \mu\text{g/L}$  and transferrin saturation  $> 50\%$  had a higher incidence of painful episodes per year (64% vs. 38%), organ failure (71% vs. 19%), and mortality (64% vs. 5%). Patients who died had significantly higher mean levels of serum ferritin than the surviving patients (2,379 versus 597  $\mu\text{g/L}$ ,  $p < 0.05$ ). The results of this study indicate that iron overload is a determinant of morbidity and mortality in adult patients with SCD ([Ballas SK. 2001](#)). Results from a natural history study demonstrated that the unadjusted death rate of transfused patients with SCD (7.0/100 person years) was even higher than in patients with thalassemia (2.2/100 person years) ([Fung EB et al. 2007](#)). Iron metabolism and trafficking in patients with SCD have some distinctive characteristics. The high levels of inflammatory cytokines in SCD may enhance macrophage/reticuloendothelial cell iron and/or renal cell iron retention. This makes tissues that retain iron different in SCD, and thus the organs that fail due to excess iron load in patients with SCD are somewhat different from those of patients with thalassemia ([Walter PB et al. 2009](#)). Indeed, unlike thalassemia patients, cardiac iron overload is not frequently observed in patients with SCD ([Kaushik N et al. 2012](#)). Nonetheless, cardiac siderosis does occur in some transfused SCD patients who have been transfused for more than 10 years ([Wood JC. 2008](#)).

Care for SCD now commonly uses transfusion, which potentially results in iron overload and necessitates chelation ([Walter PB et al. 2009](#)).

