#### **8.2.4.1 Definition of Medical/Adverse Events**

**Medical Event:** Any new untoward medical occurrence or worsening of a pre-existing condition in a patient that occurs after signing the ICF but before receiving an investigational product.

**Adverse Event:** An AE is any untoward medical occurrence in a clinical investigation in a patient administered a pharmaceutical or other therapeutic product, not necessarily

having a causal relationship with this treatment. An AE can therefore be any unfavourable and unintended sign, symptom or disease temporally associated with the use of a product, whether or not considered related to that product.

An AE does include:

- exacerbation of a pre-existing illness. This includes acute episodes/crisis of a chronic underlying condition.
- an increase in frequency or intensity of a pre-existing episodic event or condition
- a condition detected or diagnosed after study treatment administration, even though it may have been present prior to the start of the study
- a continuous persistent disease or symptom present at baseline that worsens following the start of the study

An AE does not include:

- a pre-existing disease or condition present or detected at the start of the study that does not worsen
- surgical procedures that had been planned prior to enrolment into the study
- the disease or disorder being studied, or a sign or symptom associated with the disease or disorder, unless it has worsened
- an overdose of either the study treatment or concurrent medication without any signs of symptoms

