#### 8.2.4.3 Procedures for Adverse/Medical Event Monitoring and Recording

MEs will be collected from the time the ICF is signed, and AEs will be collected from the time the treatment starts. The AEs and SAEs related to the underlying condition will be recorded separately.

Patients will be instructed to report AEs/MEs to the Investigator. Reports of adverse events will be elicited using a verbal probe and recorded in the source documentation and on the Adverse Event page of the eCRF. The Investigator or delegate should always ask the same open-ended and non-leading verbal questions of the patient to inquire about AE/ME occurrence. Appropriate questions include:

“How are you feeling?” or “How do you feel?” or for pediatric patients, “How does your child seem to feel?”

“Have you had any (other) medical problems since your last visit/assessment?” or “Have you felt any different in any way since starting the new medication/treatment or since your last visit/assessment?” or for pediatric patients, “Has your child had any (other) medical problem or seemed to act differently in any way since his/her last visit/assessment?”

“Have you taken any new medicines, other than those provided in this study, since your last visit/assessment?” or for pediatric patients, “Has your child needed to take any medicines, other than those provided in this study, since his/her last visit/assessment?”

Based on the patient’s response to these questions, the Investigator should ask additional questions relevant to the specific complaint, such as:

- How severe is/was the symptom?
- How often did the symptom occur?
- How long did the symptom last?

All AEs/MEs will be recorded and evaluated by the Investigator for their seriousness, severity, and relationship to the investigational product or study.

The Investigator should attempt to establish a diagnosis of the AE based on signs, symptoms, and/or other clinical information. Wherever possible, a diagnosis should be documented rather than the individual signs/symptoms.

The Investigator must also question the patient about any previously reported AEs that have not resolved.

The Investigator will then rate the intensity, seriousness, and causality of the AEs and will also document any measures taken to address the AE. Causality should be rated in terms of relationship to the study medication as follows: not related, possibly related, probably related, definitely related. See [Section 8.2.4.4](#) for further definitions of

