### 11.2.3 Safety Endpoints

- Frequency, severity and time to onset/duration of adverse events (AEs);
- Frequency of serious adverse events (SAEs);
- Discontinuation due to AEs;
- Hematology assessments including hemoglobin, total WBC, ANC and platelets;
- Blood serum clinical biochemistry assessments;
- 12-lead ECG.

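### No event count or exposure-adjusted rate is planned for any single adverse event term, so a moderate difference in repeat sickle cell crises is strongly attenuated

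*Protocol*

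**What the plan says.** Protocol 8.2.4.1 lists what counts as an AE. Exacerbation of a pre-existing illness is included, and the protocol adds: "This includes acute episodes/crisis of a chronic underlying condition". So is "an increase in frequency or intensity of a pre-existing episodic event or condition". Protocol 11.4.1.4 carries the idea into the analysis, covering "AEs that occurred or worsened (increased in severity and/or frequency) on or after the first dose of study medication". Section 11.2.3 puts AE frequency first among the safety endpoints.

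The counting rules in 11.4.1.4, repeated in SAP 8.1, are that "patients who experienced the same AE multiple times will only be counted once for the corresponding preferred term" and, likewise, "if a patient experiences multiple AEs within the same SOC, that patient will be counted only once for that SOC". The summaries by severity, seriousness and relationship also count each patient once.

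The shell of SAP Table 14.3.1.2 has one row per organ class and preferred term, showing number and percent of patients with a Fisher p-value. Tables 14.3.1.3 to 14.3.1.7, including serious AEs, follow the same layout. The header gives one total of events and one total of patient-years per arm. SAP 8 and 14.3 call for the same tables in sickle cell patients alone.

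Protocol 8.2.4.3 says: "The AEs and SAEs related to the underlying condition will be recorded separately". Neither document describes an analysis of those records.

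**The concern.** At least 80% of the patients are to have sickle cell disease, in which painful crises recur. In the planned crisis row, a patient with one crisis and a patient with six look the same. If one arm has more crises per patient, the row moves only as far as additional patients have a first crisis. Repeat crises go into the pooled total, where all other AEs dilute them.

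The plan thus defines a rise in frequency as an AE and names frequency as an endpoint, but no planned table gives the number or rate of crises. At stake is how well the trial can describe one recurrent safety outcome. The primary LIC comparison is not affected.

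**Working it through.** **The plan's own safety figures.** These are chances of at least one event, 1 - (1 - p)^n.

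- n = 300: 1 - 0.98^300 = 99.8% (stated as above 99%); 1 - 0.99^300 = 95.1% (stated as above 95%).
- n = 213 (SAP sample size section): 1 - 0.98^213 = 98.6% (stated 98%); 1 - 0.99^213 = 88.2% (stated 88%).

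All reproduce. They concern seeing a first event at all and say nothing about a recurrent rate or a difference between arms.

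**Inputs for the illustration.**

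- 119 deferiprone and 59 deferoxamine sickle cell patients (SAP sample size section).
- One year each, from the 52-week treatment phase. This is optimistic, because the 213 include withdrawn patients.
- Share of controls with at least one crisis: 38% and 64%, assumed. Protocol 1.1 gives these two figures for painful episodes per year in hospital patients without and with iron overload. I read them as percentages of patients.
- Dispersion k (variation between patients) of 0, 0.5 and 1, assumed.
- True rate ratio 1.5 and two-sided 5% level, assumed. The documents set neither for crises.

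**Step 1, control rate m2.** m2 = -ln(1 - p) for k = 0, otherwise m2 = [(1 - p)^(-k) - 1]/k. For p = 0.64: 1.02, 1.33 and 1.78 per year at k = 0, 0.5 and 1. For p = 0.38: 0.48, 0.54 and 0.61.

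**Step 2, what the crisis row would show.** With m1 = 1.5 x m2, the affected share is 1 - exp(-m1) for k = 0, otherwise 1 - (1 + k m1)^(-1/k). For p = 0.64 and k = 1, m1 = 2.67 and the share is 1 - 1/3.67 = 72.7%. The row shows 72.7/64 = 1.14 instead of 1.5.

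**Step 3, power.** For the planned test, Fisher on patients affected. For rates, a comparison of log mean counts with empirical between-patient variance. Simulated results:

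| Controls affected | k | Deferiprone affected | Ratio shown in row | Fisher power | Rate power |
|---|---|---|---|---|---|
| 38% | 0 | 51% | 1.35 | 34% | 47% |
| 38% | 0.5 | 49% | 1.30 | 27% | 41% |
| 38% | 1 | 48% | 1.26 | 21% | 38% |
| 64% | 0 | 78% | 1.22 | 48% | 79% |
| 64% | 0.5 | 75% | 1.17 | 30% | 68% |
| 64% | 1 | 73% | 1.14 | 21% | 57% |

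Check without simulation for the last row: variance of the log rate ratio = (1/2.67 + 1)/119 + (1/1.78 + 1)/59 = 0.0116 + 0.0265 = 0.0380, SE 0.195, z = ln(1.5)/0.195 = 2.08, power = Phi(2.08 - 1.96) = 55%. Exact Fisher power there is 20%. Over all six rows this route gives 20-49% for Fisher and 37-78% for rates, agreeing with the simulation within its error.

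**Step 4, a larger effect.** For a true doubling, exact Fisher power is 93%, 69% and 47% at p = 0.64 (k = 0, 0.5, 1) and 81%, 66% and 53% at p = 0.38. The rate comparison has 81% or more throughout.

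**Step 5, the pooled header total.** If other AEs run at an assumed rate o per patient-year and crises at c, a 1.5-fold crisis rise changes the overall rate by (1.5c + o)/(c + o). For c = 1, o = 20: 21.5/21 = 1.02. For c = 3, o = 5: 9.5/8 = 1.19. The pooled rate moves by 2-19%, and no comparison of it is planned.

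**The case against.** Counting each patient once per term is conventional. Safety analysis here is mainly descriptive, with no alpha or power target, so test power is not a standard the plan sets itself. That is fair, and it is why the remedy should be an estimate with an interval and not another test. It does not explain why the tables lack per-term event counts.

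A reader might infer that repeat events are ignored altogether. They are not: total AEs and exposure are reported per arm, also for sickle cell patients alone, AE listings per patient are planned, and SAP 17 allows tables to depart from the shells. What is missing is anything per term.

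A reader might also infer that a rise in crises would be invisible, or the patient percentage stuck near its ceiling. Under the inputs used here neither follows: 64% against 78% is a visible gap, and a doubling is often detected.

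The inputs are weakly tied to this trial. The 64% describes iron-overloaded hospital patients, whereas the trial enrols transfused patients from age 2, and transfusion is given partly to prevent crises. At 38% the advantage of rates is smaller and the rate comparison is itself underpowered for a 1.5-fold rise. This stands, and is why a range is given.

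Two further readings lack support. The documents do not make crisis rate a main safety question: the one AE of special interest is neutropenia. Nor do they show that unequal drop-out would distort the percentages. Exposure could differ between arms, but no figure is given.

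The most serious objection is about recording. Protocol 8.2.4.1 counts crises as AEs, excludes signs of the studied disease unless worsened, and treats a rise in frequency as an AE in itself. One site might enter six crises and another a single worsening, in an open-label trial. This limits any record-based rate and has to be met in the fix.

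**Conclusion.** The gap is real but narrower than it first looks. No event count or exposure-adjusted rate is planned for any single preferred term, although the protocol makes crises and a rise in frequency AEs and names AE frequency as an endpoint. That follows from the text alone.

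The size is conditional. For a true rate ratio of 1.5, the crisis row would show a ratio of about 1.14 to 1.35, with power of about 21-48% for the planned test against 38-79% for a rate comparison. Rates do better in every setting examined, but the figures rest on assumed crisis frequency and dispersion, a full year of follow-up, and each crisis being recorded as an event. The right word is attenuated. The change is worth making before database lock; it is not a threat to the trial's main conclusion.

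**What to change.** Keep the patient counts. In protocol 11.4.1.4, SAP 8.1 and Tables 14.3.1.2 and 14.3.1.6, add for each preferred term and arm the number of events and events per 100 patient-years.

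For sickle cell crisis in sickle cell patients, prespecify one descriptive rate ratio (deferiprone/deferoxamine) with 95% CI, from a negative binomial model with log exposure as offset. State which preferred terms count as crisis, include the underlying-condition AEs that are recorded separately, and fix a rule for merging records of one episode.

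The cost is two columns per arm in existing tables and one model, using AE and exposure data already collected. Expect limited precision: with the standard errors at a ratio of 1.5 (0.149 to 0.249), the interval multiplies and divides the estimate by exp(1.96 x 0.149) = 1.34 to exp(1.96 x 0.249) = 1.63. The rate will also depend on how sites record and split episodes in an open-label trial, so label it a supportive safety estimate.
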